Table of Tables

Table 1: FMT dosing and associated risks	12
Table 2: Schedule of study procedures	26

List of Abbreviations

AE: Adverse event

AESI: Adverse event of special interest

AFT: accelerated failure time

ANC: Absolute neutrophil count

BMI: body mass index

CDI: *Clostridium difficile* infection

CCH: Chester County Hospital

CFR: Code of federal regulations

CFU: colony-forming units

CRC: clinical research coordinator

DSMB: Data safety monitoring board

EIA: enzyme immunoassay

FMT: Fecal Microbiota Transplantation

g: grams

HIPAA: Health Insurance Portability and Accountability Act of 1996

HUP: Hospital of the University of Pennsylvania

ICH: International Conference on Harmonisation

IDSA: Infectious Diseases Society of America

ITT: intention to treat

LGH: Lancaster General Hospital

m-ITT: modified intention to treat

mL: milliliters

NAAT: nucleic acid amplification testing

PAH: Pennsylvania Hospital

PHI: protected health information

PMPMC: PennMedicine Princeton Medical Center

PMT: Penn Microbiome Therapy

PPI: proton pump inhibitor

PPMC: Penn-Presbyterian Medical Center

R-CDI: Recurrent *Clostridium difficile* infection

SAE: Serious Adverse Event

SIRS: systemic inflammatory response syndrome

S/SC/F-CDI: severe or severe-complicated/fulminant *Clostridium difficile* infection

SUSAR: Suspected unexpected serious adverse reaction

WBC: white blood cells

Study Summary

Title	A Phase II, Randomized Trial to Evaluate the Optimal Dosing of Fecal Microbiota Transplantation using the Penn Microbiome Therapy Products for Recurrent Clostridium difficile Infection
Short Title	PMT for Recurrent-CDI
IRB Number	832963
Phase	Phase II
Methodology	Randomized, open label, comparative
Study Duration	Two years
Study Center	PennMedicine -- University of Pennsylvania Health System
Objectives	
Primary: To evaluate the efficacy of fecal microbiota transplantation (FMT) performed using the Penn Microbiome Therapy (PMT) suite of products to treat subjects with recurrent Clostridium difficile infection (R-CDI) by comparing the clinical outcomes of two treatment strategies: (1) single-dose PMT; (2) two doses of PMT administered within 24 hours.Secondary: To determine whether mass of fecal material or quantitative culture better predicts efficacy of PMT products used to treat subjects with R-CDI.Exploratory: To characterize differences in the efficacy of fecal microbiota transplantation for R-CDI based on route of administration, unique bacterial community features of the administered PMT dose, and host immune response to infection.
Number of Subjects	Target enrollment: 300 subjects.

Main Inclusion and Exclusion Criteria

Inclusion Criteria:

1. Second or greater episode of CDI (first or greater recurrence) within 12 months, with symptoms including bowel movements altered in frequency or consistency from baseline.
2. Stool positive for *C. difficile* toxin by EIA or toxin gene by NAAT within 60 days of enrollment.
3. At least one additional prior positive stool test for *C. difficile* within the prior 12 months (EIA or NAAT as above).
4. Age \geq 18 years.
5. Minimum of 72 hours of receipt of standard-of-care (vancomycin or fidaxomicin) antibiotic treatment for R-CDI prior to intervention.

Exclusion Criteria:

1. Evidence of colon/small bowel perforation at the time of study screening
2. Goals of care are directed to comfort rather than curative measures.
3. Moderate (ANC < 1000 cells/uL) or severe (ANC < 500 cells/uL) neutropenia.
4. Known food allergy that could lead to anaphylaxis.
5. Pregnancy
6. Meeting criteria for S/SC/F-CDI within 24 hours of planned trial enrollment, which we define as any one of the following: (1) leukocytosis with peripheral WBC $\geq 15,000$ cells/mL; (2) hypotension with systolic blood pressure sustained < 90 mmHg for three or more hours or requiring pressors; (3) provider documentation of ileus or radiologic evidence of bowel dilation or megacolon; (4) acute kidney injury with increase in baseline serum creatinine level by $\geq 50\%$ or new dialysis initiation; (5) serum lactate > 2.2 mmol/L; or (6) ≥ 3 systemic inflammatory response syndrome (SIRS) criteria (which include heart rate > 90 beats per minute, respiratory rate > 20 breaths per minute or $\text{PaCO}_2 < 32$ mmHg, temperature $> 38^\circ\text{C}$ or $< 36^\circ\text{C}$, WBC $> 12,000$ cells/uL, $< 4,000$ cells/uL, or $> 10\%$ immature (band) forms).
7. Receipt of FMT or enrollment in a clinical trial for FMT within the last 3 months.

Investigational Product	
1. Penn Microbiome Therapy – 001 (PMT-001): no more than 152 mL suspension for rectal enema from 40g human stool, comprising a total of 1×10^8 – 1×10^{12} anaerobic bacterial CFUs/dose.2. Penn Microbiome Therapy – 002 (PMT-002): no more than 152 mL suspension for intragastric, intraduodenal, or intrajejunal administration from 40g human stool, comprising 1×10^8 – 1×10^{12} anaerobic bacterial CFUs/dose.3. Penn Microbiome Therapy – 003 (PMT-003): no more than 32 capsules for oral administration from 40g donated stool, comprising 1×10^8 – 1×10^{12} anaerobic bacterial CFUs/dose.
	PMT-001, PMT-002, PMT-003, are packaged for single-dose administration.
Duration of administration	10 – 90 minutes (target 30 minutes)
Reference therapy	Single dose of Penn Microbiome Therapy product.
Statistical Methodology	Primary outcome will be resolution of diarrhea without recurrence assessed at 8 weeks (56 days) after intervention. Logistic regression analysis will be used to assess if repeat dosing is superior to single dose.
Safety Evaluations	We will monitor safety of administration as well as safety of the investigational products, in terms of adverse events as listed in Section 9 .
Data and Safety Monitoring Plan	See Section 10 .

Background and Study Rationale

This study will be conducted in full accordance all applicable University of Pennsylvania Research Policies and Procedures and all applicable Federal and state laws and regulations including 45 CFR 46, 21 CFR Parts 50, 54, 56, 312 and Good Clinical Practice: Consolidated Guidelines approved by the International Conference on Harmonisation (ICH). All episodes of noncompliance will be documented.

1. Introduction

Fecal microbiota transplantation (FMT) is recommended treatment for recurrent *Clostridium difficile* infection (R-CDI) based on its success in multiple trials targeting subjects with mild or moderate CDI symptoms (McDonald 2018; Kelly BJ 2018). FMT product dosing has typically been defined by the mass of human stool used to generate the dose. However, the FMT products used to treat R-CDI are not standardized, and trials to date have demonstrated a large range of efficacy (Cammarota 2014; van Nood 2013; Youngster 2016; Kelly CR 2016). A recent trial utilizing a greater mass of starting stool material demonstrated greater efficacy than prior trials (Kao 2017), raising the question of how the mass of stool material used to generate FMT product contributes to the efficacy of the product. Another possible explanation for the varying efficacy of FMT products is the fact that they originate from different stool donors, each with a unique gut microbiome and concentration of microbes (Seekatz 2014). We will perform a randomized controlled trial to evaluate the safety and efficacy of Penn Microbiome Therapy (PMT) products for FMT in subjects with R-CDI. The PMT products comprise three different formulations of FMT for oral, enteric (via tube), or rectal delivery. The trial will compare the efficacy of standard-dose FMT (a single dose derived from 40g starting stool mass administered once) versus double-dose FMT (i.e., two single doses, or the equivalent of 80g starting stool mass, administered within 24 hours) in the treatment of R-CDI. We will further evaluate the concentration of anaerobic bacteria, which include the taxa most frequently identified as protective against CDI (Lee YJ 2017), in FMT products to determine whether administered stool mass or bacterial concentration better predict FMT efficacy. We will also explore microbiome differences between FMT donors and differences in host immune response to CDI predictors of FMT efficacy. There is no placebo arm in the trial because FMT is already established as recommended therapy for R-CDI.

1.1. Background and Relevant Literature

As recently as 2015, the Centers for Disease Control and Prevention (CDC) identified *Clostridium difficile* infection (CDI) as an “urgent” threat associated with upwards of 500,000 infections in the United States each year and resulting in over 15,000 deaths. CDI is characterized by a clinical syndrome that typically includes loose, frequent bowel movements and abdominal pain, which occur as a result of toxin production by colonic *C. difficile*. CDI occurs in patients colonized with toxigenic *C. difficile* and in patients who have newly acquired *C. difficile*. Estimates of the relative contributions of persistent colonization and new acquisition to incident CDI vary. In both cases, the pathogenesis of CDI involves depletion of non-*C. difficile* colonic microbiota, altered bile acid metabolism, germination of (resident or recently ingested) *C. difficile* spores, expansion of a population of vegetative *C. difficile*, toxin production, and colonic inflammation. Key challenges

associated with CDI include its recurrence after appropriate antibiotic treatment (R-CDI), and its progression to a more severe disease state with systemic signs of inflammation or even sepsis. The latter, termed severe or severe-complicated/fulminant CDI (S/SC/F-CDI), often requires extended hospitalizations, may require colectomy, and is associated with high rates of mortality (Kelly BJ 2018). At present, antibiotic treatment is the recommended therapy for early R-CDI, and antibiotic treatment followed by FMT is the recommended therapy for later R-CDI. Antibiotics are the recommended therapy for S/SC/F-CDI (McDonald 2018).

1.2. Name and Description of the Investigational Product

Penn Microbiome Therapy suite of investigational products

- Penn Microbiome Therapy – 001, hereafter referred to as PMT- 001
 - Dose: 1×10^8 – 1×10^{12} anaerobic bacterial CFUs derived from 40g of human stool diluted with 10% glycerol into no more than 152 mL suspension of investigational product.
 - Enema administered rectally
- Penn Microbiome Therapy – 002, hereafter referred to as PMT - 002,
 - Dose: 1×10^8 – 1×10^{12} anaerobic bacterial CFUs derived from 40g of human stool diluted with 10% glycerol into no more than 152 mL suspension of investigational product.
 - Suspension administered intragastric, intraduodenal, or intrajejunal
- Penn Microbiome Therapy – 003, hereafter referred to as PMT - 003,
 - Dose: 1×10^8 – 1×10^{12} anaerobic bacterial CFUs derived from 40g of human stool diluted with 10% glycerol and concentrated to fill no more than 32 capsules
 - All 32 capsules to be administered orally

Chemical Name and Structure:

PMT-001: Fecal Microbiota for Transplant, enema product

PMT-002: Fecal Microbiota for Transplant, suspension product

PMT-003: Fecal Microbiota for Transplant, capsule product

The three investigational products, PMT-001,002, 003, are composed of donated stool from healthy donors that meet the donation criteria. The stool sample is composed of approximately 75% water and 25% organic and inorganic solids. Typically, 1g of stool contains approximately 10^9 bacterial cells. The stool sample is subsequently processed with phosphate-buffered saline (PBS) containing 10% glycerol and formulated as a suspension for PMT-001 and PMT-002 or concentrated and encapsulated for PMT-003.

1.2.1. Non-Clinical Data

FMT as a treatment modality for CDI did not take the conventional path of drug development. Fecal transplants seem to date as far back as 4th century China, and have recently become recommended therapy for R-CDI on the basis of several randomized trials (McDonald 2018; van Nood 2013; Youngster 2016; Kelly CR 2016; Kao 2017), even as there remains significant heterogeneity among FMT products. There is no established standard for non-clinical testing of FMT products given uncertainty as to what microbial features determine potency (Bojanova 2016). The treatment protocol outlined here is based on the results published from prior studies that have driven the standards adopted in our R-CDI and S/SC/F-CDI protocols (Hamilton 2012; Kelly BJ 2018; Cammarota 2017; Krajicek 2018).

1.2.2. Clinical Data to Date

There is no available clinical research data to date on the investigational products PMT-001, 002 or 003. FMT has been established as effective and is recommended for treatment of multiply recurrent CDI on the basis of several randomized controlled trials (McDonald 2018; van Nood 2013; Youngster JAMA 2014; Kelly CR 2016; Kao 2017). See [Table 1](#) for a summary of the risks described in the literature.

Table 1: FMT dosing and associated risks.

Authors	Publication Year	Population	Study Design	FMT Dose (g stool)	FMT Formulation	FMT Administration	Risks
Hamilton et al	2012	R-CDI	single-group trial	50g stool	250mL suspension	colonoscopy	diarrhea, flatulence
van Nood et al	2013	R-CDI	randomized trial	(not reported)	500mL suspension	duodenal tube	diarrhea, cramping, belching
Youngster et al JAMA	2014	R-CDI	single-group trial	48g stool	30 capsules	oral	cramping, bloating
Kelly et al	2016	R-CDI	randomized trial	64g stool	500mL suspension	colonoscopy	chills, abdominal pain, bloating, nausea, flatulence
Kao et al	2017	R-CDI	randomized trial	80-100g stool	40 capsules or 180mL suspension	oral or colonoscopy	nausea, vomiting, fever, abdominal discomfort
Weingarden et al	2013	R-CDI	case series	50g stool	250mL suspension	colonoscopy	(not reported)
Agrawal et al	2015	R-CDI	case series	~30-60g stool	150-500mL suspension	upper endoscopy, lower endoscopy, enema	diarrhea, constipation, abdominal pain, ileus
Aroniadis et al	2015	R-CDI	case series	(not reported)	suspension	upper endoscopy, lower endoscopy, enema, colonoscopy	diarrhea, abdominal pain
Fischer et al	2015	R-CDI	case series	50-100g stool	300mL suspension	sigmoidoscopy or colonoscopy	treatment failure and death
Fischer et al	2017	R-CDI	case series	50-100g stool	300mL suspension	sigmoidoscopy or colonoscopy	treatment failure and death

1.3. Dose Rationale

There are no pre-clinical or clinical data for the PMT suite of FMT products to inform optimal dose. However, there are extensive observational studies and several randomized trials that suggest an FMT dose derived from 30-100g of human stool is effective to treat R-CDI (Cammarota 2014; van Nood 2013; Youngster JAMA 2014; Kelly CR 2016). A recent trial utilizing a greater mass (80-100g) of starting stool material demonstrated greater efficacy than prior trials (Kao 2017), raising the question of how the mass of stool material used to generate FMT product contributes to the efficacy of the product. We will evaluate the safety and efficacy of PMT products for FMT to treat R-CDI, comparing single-dose (40g starting stool mass) versus double-dose (i.e., two PMT doses administered within 24 hours). The PMT products produced from these 40g stool mass contain a range of 1e8 – 1e12 anaerobic bacterial CFUs, so the double-dose intervention will contain twice that. Though the difference in anaerobic CFUs is marginal between single and double-dose interventions, other bacterial taxa may scale more directly with stool mass, and recent trial data (Kao 2017) suggest that such a difference might be clinically meaningful.

2. Study Objectives

2.1. Primary Objective

To evaluate the efficacy of fecal microbiota transplantation (FMT) performed using the Penn Microbiome Therapy (PMT) suite of products to treat subjects with recurrent *Clostridium difficile* infection (R-CDI) by comparing the clinical outcomes of two treatment strategies: (1) single-dose PMT; (2) two doses of PMT administered within 24 hours.

2.2. Secondary Objective

To determine whether mass of fecal material or quantitative culture better predicts efficacy of PMT products used to treat subjects with R-CDI.

2.3. Exploratory Objective

To characterize differences in efficacy of fecal microbiota transplantation for R-CDI based on (1) route of administration, (2) unique bacterial community features of the administered PMT dose, and (3) features of host immune response to CDI.

3. Investigational Plan

3.1. General Design

We will perform a randomized, controlled, open label trial. Subjects will be screened to evaluate if they meet inclusion criteria for recurrent CDI. If eligible, subjects will participate in the informed consent process. Following informed consent subject preference and guidance of the referring/primary care team will be used to identify route of administration. Stratified randomization will then be used by route of administration to randomize subjects to one of two

arms: (1) single dose of PMT, or (2) two doses of PMT administered within 24 hours. We will compare the two treatment strategies' success in achieving clinical resolution of diarrhea in subjects with R-CDI. Subjects randomized to receive two doses of FMT will receive two doses from the same donor (but not necessarily from the same manufacturing batch). The route of administration may be different for the second dose per subject's treating physician and subject preference. Subjects will be followed until 180 days after their last PMT dose.

3.1.1. Screening Phase

Because FMT is recommended therapy for R-CDI, potential subjects will be identified through active screening and by referral from a care provider within the University of Pennsylvania Health System (PennMedicine). Potential subjects' health records will be initially screened by a study team member to evaluate if the inclusion/exclusion criteria may be met. If a potential subject may meet inclusion/exclusion criteria, the potential subject (or their designated medical decision- maker) will be contacted in person or by telephone to discuss participation. If a potential subject is currently admitted to the hospital and if the primary team is not already aware of potential eligibility, the study team will contact the subject's inpatient care team to ascertain whether the care team has any objection to the study team enrolling the potential subject. The potential subject (or their designated medical decision-maker) will be contacted to discuss participation, final screening for inclusion/exclusion criteria will be performed, and informed consent will be obtained.

3.1.2. Study Intervention Phase

R-CDI trial interventions may be performed inpatient or outpatient at the listed study sites in [section 4.5](#). Once subjects are enrolled and informed consent is obtained, subjects will be assessed for their ability to tolerate oral capsules, gastric/duodenal/jejunal infusion, and enema (per active prescribed medication list and/or opinion of referring care provider); the subject's preference and the guidance of the referring care provider will determine if PMT-001, PMT-002, or PMT-003 will be used. Following this, stratified randomization to single- or double-dose strategy will be performed within route of delivery groups (i.e., within PMT-001, PMT-002, or PMT-003 groups). Administration of a single dose of the product will take place over 10 to 90 minutes (target 30 minutes). A second dose will be given between 4 and 24 hours after the first dose. The route of administration may be different for the second dose per subject's treating physician and subject preference. If a subject is unable to take at least 50% of a dose, they will be permitted to opt to receive a different route of administration for one dose within 24 hours. Any antibiotics previously prescribed for the treatment of CDI will be stopped 12-48 hours (target 24 hours) prior to the intervention.

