3.1.5. Allocation to Interventional Group

Stratified randomization will be performed in a 1:1 fashion (one to single-dose and one to double-dose). The stratification will be by route of delivery, which will be decided on following enrollment but prior to randomization. The route of administration (i.e., PMT-001 versus PMT-002 versus PMT-003) will be determined by counsel from the subject's referring health care provider and the subject's own preference. The randomization strata will include: upper delivery (PMT-002 or PMT-003) or lower delivery (PMT-001). Stratified randomization by route will be performed in order to ensure balance in route of delivery between the two groups. The randomization schedule will be prepared using a random-size block strategy to ensure balance throughout the trial. Prior to enrollment of the first subject, a randomization table will be produced for each category using Stata statistical software and the "Ralloc" package. There is no randomization to a no-FMT control because FMT is already guideline-recommended for the treatment of R-CDI (McDonald 2018).

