5.7. Administration and Accountability

The investigational products will be checked on receipt as above ([Section 5.3](#)). Prior to administration, PMT-001 and PMT-002 will be allowed to thaw at room temperature (50°F - 75°F) for 30-60 minutes. Administration of PMT-001 and PMT-002 will begin within 60 minutes of thawing. Prior to administration, PMT-003 will be kept on dry ice; PMT-003 will not be thawed before administration.

As stated in [Section 5.4](#), the total time from release from frozen storage at the manufacturing facility to initiation of administration will not exceed 180 minutes for PMT-001 and PMT-002; it will not exceed 120 minutes for PMT-003.

The duration of administration will take 10 - 90 (target 30) minutes for all products. Administration of all three PMT products will be performed by a licensed physician, advanced medical practitioner, or nurse.

PMT-001 will be administered by enema using an approved enema administration kit. PMT-002 will be administered via intragastric, intraduodenal, or intrajejunal route, contingent on the presence of a pre-existing approved intragastric, intraduodenal, or intrajejunal tube. PMT-003 will be administered orally. Post-procedure monitoring will be performed as described

elsewhere. For each investigational product dose, the product identity, dose targeted for administration, the date and time administered, route of administration, subject identity, quantity of product actually administered, and quantity of product remaining will be recorded via a standard form.

5.8. *Subject Compliance Monitoring*

Post-procedure monitoring will be performed as described elsewhere ([Sections 3.1.3](#) to [Section 3.1.4](#)). For each investigational product dose, the product identity, dose targeted for administration, the date and time administered, route of administration, subject identity, quantity of product actually administered, and quantity of product remaining will be recorded via a standard form. The study team will record if the subject was not able to tolerate or receive the full dose due to adverse events or because the allowed duration of administration was exceeded.

5.9. *Return or Destruction of Investigational Product*

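### Section 3.1.2 stratifies the randomization by three products and Section 3.1.5 by two delivery strata; under two strata, between-arm balance of PMT-002 subjects is not assured

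*Combined protocol and SAP*

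**What the plan says.** Section 3.1.2 places the randomization to single or double dose "within route of delivery groups (i.e., within PMT-001, PMT-002, or PMT-003 groups". That is three strata.

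Section 3.1.5 reads differently: "The randomization strata will include: upper delivery (PMT-002 or PMT-003) or lower delivery (PMT-001". That is two strata. The same section describes route by product ("The route of administration (i.e., PMT-001 versus PMT-002 versus PMT-003) will be determined by counsel") and gives the purpose of stratifying: "Stratified randomization by route will be performed in order to ensure balance in route of delivery between the two groups". Allocation is 1:1 in blocks of random size, and "a randomization table will be produced for each category using Stata statistical software". The number of categories is not stated.

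Section 6.1.5 refers to Section 3.1.5 for the procedure. Sections 3.1 and 5.2 say only that randomization is stratified by route. Under Section 5.7, PMT-002 is "contingent on the presence of a pre-existing approved intragastric, intraduodenal, or intrajejunal tube", whereas PMT-003 is up to 32 oral capsules (Section 1.2). The primary model in Section 8.4.2 is a logistic regression stratified by the most recent positive test (NAAT or EIA). It names no route or product term.

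**The concern.** Three strata and two strata need different sets of randomization tables, so tables that follow one section depart from the other. Someone who must generate, audit or analyze the randomization cannot tell from the protocol which strata apply.

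Section 3.1.5 also falls short of its own purpose. With PMT-002 and PMT-003 in one list, the blocks balance the arms for the two products taken together. The split of PMT-002 subjects between arms is then right in expectation but not enforced. The two products reach different subjects, since one requires a tube already in place and the other requires swallowing capsules. The documents do not say whether cure rates differ between them, but Section 2.3 treats efficacy by route as an open question. If they do differ, the primary model has no term to absorb a chance imbalance.

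**Working it through.** **1. The text side by side.**

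| Section | Grouping for randomization | Number of strata |
|---|---|---|
| 3.1.2 | PMT-001; PMT-002; PMT-003 | 3 |
| 3.1.5, strata sentence | PMT-002 with PMT-003; PMT-001 | 2 |
| 3.1.5, description of route | PMT-001; PMT-002; PMT-003 | not a strata statement |
| 6.1.5 | refers to 3.1.5 | 2, by reference |
| 3.1 and 5.2 | by route, not defined further | unspecified |

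**2. The plan's own figures.** Section 8.3 gives detectable cure rates, against 50% at 80% power and a two-sided type I error of 0.2, of 71.33% (EIA, 45 per arm) and 65.43% (NAAT, 90 per arm). With unpooled variance, power = Φ(d / √[(p₁q₁ + p₂q₂)/n] − 1.2816).

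- EIA: √[(0.25 + 0.7133 × 0.2867)/45] = 0.1005; 0.2133/0.1005 − 1.2816 = 0.841; power 79.98%.
- NAAT: √[(0.25 + 0.6543 × 0.3457)/90] = 0.0727; 0.1543/0.0727 − 1.2816 = 0.840; power 79.95%.

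Both reproduce. Route strata do not enter the calculation, so no choice of scheme changes them.

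**3. How far PMT-002 can drift.** The documents give neither block sizes nor product shares. Assumed here: blocks of 2, 4 or 6; an upper stratum of 150, 200 or 250; and 10 to 60 PMT-002 subjects placed at random within it. There were 3,000 simulated randomizations per setting. Results for an upper stratum of 200:

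| PMT-002 subjects | Mean absolute arm difference | 95th percentile | Chance of 60:40 or worse | Chance of 70:30 or worse |
|---|---|---|---|---|
| 10 | 2.4 | 6 | 75% | 33% |
| 20 | 3.4 | 8 | 49% | 10% |
| 30 | 3.9 | 10 | 31% | 3% |
| 60 | 5.1 | 12 | 9% | 0% |

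Over all three stratum sizes the mean difference runs from 2.3 to 5.4 and the 95th percentile from 6 to 14. With a separate PMT-002 list the difference never exceeded 2. A final block of 6 left incomplete can differ by at most 3, and the even counts used here hold it to 2.

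**4. What that costs in precision.** Assume 30 PMT-002 subjects, 150 randomized per arm, and a cure rate 20 to 30 points lower in PMT-002 subjects. The 30 and the deficit are assumptions with no source in the documents. Treating the split as binomial, which slightly overstates its spread under blocking:

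- SD of the arm difference = √30 = 5.5 subjects.
- Shift in the cure-rate difference = 5.5 × 0.20 to 0.30 / 150 = 0.7 to 1.1 points.
- Overall cure rate from Section 8.3 = (2 × 0.50 + 0.70)/3 = 0.567; standard error = √(2 × 0.567 × 0.433/150) = 0.057, or 5.7 points.
- Ratio = 0.13 to 0.19 standard errors; squared, about 2% to 4% of the variance.

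**The case against.** The best defense is that Section 3.1.5 governs. It alone gives the ratio, strata, blocking, tables and software, and Section 6.1.5 refers to it. The statement in 3.1.2 is a parenthesis in an overview, and two strata are a legitimate choice. This stands in part. Two strata are the likelier reading in practice, and correcting 3.1.2 would be an acceptable repair. But the cross-reference does not withdraw 3.1.2, and it does not settle the gap within 3.1.5 between route as three products and strata that separate only two groups.

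A reader might go further and infer that the dose comparison is biased or its error rate inflated. With 30 PMT-002 subjects split 20:10 and the same 20 to 30 point deficit, the shift is 10 × 0.20 to 0.30 / 150 = 1.3 to 2.0 points, or 0.23 to 0.35 standard errors. Given that split, the one-sided 0.2 test rejects falsely about 27% to 31% of the time. These figures hold only after one unfavorable draw. A 2:1 or worse split of 30 has a binomial probability of about 10%, so about 5% in the inflating direction. In the other direction the conditional rate falls to about 12% to 14%. Averaged over the randomization, the comparison is unbiased and its error rate nominal. The ordinary standard error already covers this variation.

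A reader might also infer that the exploratory objective on route is undermined. Section 2.3 asks about efficacy between routes and does not call for a dose comparison inside each route. Even for a dose comparison within PMT-002, 20:10 in place of 15:15 raises the standard error by only √(0.150/0.133) − 1, about 6%.

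**Conclusion.** The inconsistency is certain and unresolved in the current text; its statistical consequence is modest. Under Section 3.1.5, balance of PMT-002 subjects between arms is not assured, which falls short of the purpose that section states. It would be wrong to say that they are unbalanced, because 1:1 allocation balances them in expectation. The sample size and power in Section 8.3 are unaffected.

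The loss is threefold: enforced balance on one product, a small amount of precision, and a clear statement of which strata were used. The first two sizes (a 95th percentile difference of 6 to 14 subjects, and about 2% to 4% of the variance) are illustrations that rest on assumed block sizes, PMT-002 numbers and cure-rate deficit. The third needs no assumption.

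**What to change.** State one scheme in Sections 3.1.2, 3.1.5 and 6.1.5, and make it match the tables actually generated.

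- If no tables are in use, generate three lists (PMT-001, PMT-002, PMT-003) and change the strata sentence in 3.1.5. This delivers the balance in route that the section promises. The cost is one more table and one more list that may end in an incomplete block. With blocks of up to 6, the worst overall arm difference rises from 2 × 3 = 6 to 3 × 3 = 9 subjects out of 300.
- If two lists are already in use, keep them and correct the parenthesis in 3.1.2.

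In either case, add the initially chosen product as a covariate in the primary logistic model of Section 8.4.2, alongside NAAT/EIA. It should be the product settled before randomization, because Sections 3.1 and 3.1.2 allow the route to change for the second dose and a later route could depend on the assigned arm. The cost is two model parameters and an odds ratio that is conditional on product. The plan should also say what happens if PMT-002 subjects are too few to fit the term, for example by merging the two upper products.
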